## 5. Inclusion/Exclusion Criteria

Fetal, Neonatal and Infant protocol: *Inclusion criteria:* 1. Current opioid use disorder (OUD) as defined by DSM 5 criteria 2.18-44 years of age with singleton pregnancies, generally uncomplicated by conditions that jeopardize pregnancy outcome 3. Gestation less than 34 weeks

**Exclusion criteria:** 1. Complications of pregnancy, including gestational diabetes, polyhydramnios, hypertension, placenta previa or significant risk of preterm delivery; 2. Evidence of fetal malformation detected by prenatal ultrasound; 3. Significant general maternal health problems that can affect fetal functioning, including Type I or gestational diabetes, alterations in thyroid functioning, HIV infection or hypertension; 4 Significant maternal psychopathology that would preclude informed consent, such as unstable schizophrenia; 5. Alcohol use disorder per DSM 5 criteria; 6. Significant benzodiazepine use which would portend seizure activity during the induction period. This will be determined for all women reporting benzodiazepine use at the time of program intake by the project psychiatrist(s). 6. For the B+N group: Women stable on methadone maintenance (defined as more than 3 consecutive days of dosing); 7. For the B+N group: Women coming to treatment reporting “street” methadone use (for more than 3 consecutive days); 8. Women planning for adoption of their infant.

**Breastmilk protocol:** 10 B+N exposed infants and their mothers from the fetal study who meet criteria for breastfeeding (i.e. illicit drug use/licit drug misuse abstinence in the last 90 days prior to delivery or counselor endorsement of breastfeeding in the case of abstinence 30-90 days prior to delivery, HIV negative status, no concurrent prescription medication use that is contraindicated in lactation, and legal custody of their infant at delivery) will be enrolled.

**Inclusion criteria:** 1. B+N maintained mother, enrolled in parent study. 2. Free of illicit drug use and licit drug misuse after 36 weeks gestation or 30-90 days prior to delivery by standardized urine toxicology drug screening and drug treatment compliant. 3. Delivery at 37 weeks or later determined by second trimester ultrasound which is standard of care at the facility of recruitment.

**Exclusion criteria:** 1. Concurrent Axis I diagnosis, or the presence of a serious psychiatric illness that would preclude informed consent. 2. Presence of maternal medical illness or condition that would preclude or impair the infant’s ability to breast feeding. (i.e. respiratory concerns such as meconium aspiration, perinatal asphyxia, etc. These will be individually determined on a case-by-case basis). 3. Major congenital malformation or minor congenital malformation that would impair the infant’s ability to breastfeed (i.e. Pierre-Robin syndrome, cleft palate). Determined on a case by case basis. 4. Mother or infant positive for illicit substances at birth, indicating recent substance abuse and non-suitability for breastfeeding in the perinatal period (per ABM (Jansson, 2009a) guidelines). 5. Poor compliance with drug treatment and/or high risk of relapse to illicit substances as determined by mental health counselor making breastfeeding unadvisable, 6. Delivery at another institution. 7. Failure to leave specimens as per protocol.

## **6. Drugs/ Substances/ Devices**

- a. The rationale for choosing the drug and dose or for choosing the device to be used.
- b. Justification and safety information if FDA approved drugs will be administered for non-FDA approved indications or if doses or routes of administration or participant populations are changed.

There is a limited body of literature that supports the safe and efficacious use of B+N during pregnancy. Small US studies evaluating maternal and infant outcomes in B+N exposed pregnancies have found no obvious significant adverse effects related to medication use in mothers or infants (Debelak, 2013; Lund, 2013), however, both studies suffer from small *ns* (10 each). One recent study found favorable results in B+N, as compared to methadone-exposed infants in terms of reduced NAS severity in a larger cohort (*n*=62), but did not compare results to buprenorphine-only exposed infants (Weigand, 2015).

- c. Justification and safety information if non-FDA approved drugs without an IND will be administered.

NA, an amended IND was applied for (with no response from the FDA).

## **7. Study Statistics**

- a. Primary outcome variable.

*Fetal variables.* Derived fetal variables include those centered on heart rate alone, movement, and their interrelation. Cardiac variables will include FHR, FHR variability (root mean square) and FHR accelerations (i.e., episodic excursions in FHR amplitude above baseline). Movement is characterized as number of bouts, duration, and total motor activity. Linkage between the two domains of function will be quantified in two ways: somatic-cardiac (FM-FHR) coupling based on a priori criteria (i.e., the proportion of observed FMs associated with excursions in FHR of a predetermined criteria for a predetermined length of time; ([name], 1996) and through time series techniques to quantify linkage without a priori criteria ([name], 2001). With the exception of accelerations, motor bouts, and somatic-cardiac coupling which are either counts or proportions. Variables are quantified in 1-minute epochs and mean values for each 60 minute recording are used for analysis. Fetal measures will be derived at trough (just prior to dosing) and peak (2 hours after dosing) maternal buprenorphine levels.

*Maternal autonomic variables.* Maternal ECG data will undergo R-wave detection, manual editing for artifact, and quantified as heart period (interval between R-waves in msec), heart period variability (standard deviation of successive heart periods), and an indicator of respiratory sinus arrhythmia which reflects vagal, predominantly parasympathetic influences on heart rate variation (Grossman & Kollai, 1993). Maternal variables also include respiratory period (s) and skin conductance. As with the fetal data, variables are quantified in 1-minute epochs and mean values for each 60 minute recording are used for analysis.

*Neonatal variables.* The primary newborn study measures are Neonatal Abstinence Syndrome (NAS) scores as assessed every four hours for the duration of the infant's hospital stay after delivery. Variables will include mean NAS scores on days 1 through 4 minimally (all opioid exposed infants are hospitalized for a minimum of four days after delivery for observation) or for the infant's hospitalization, and highest score. NAS severity will also be quantified as the total amount of medication (oral morphine sulfate, mg) used to treat NAS, days of pharmacologic treatment required, and total days of hospital stay.

*Infant variables.* Infant testing using the NNNS generates 13 summary scores (habituation, attention, handling, quality of movement, regulation, non-optimal reflexes, asymmetric reflexes, stress/abstinence, arousal, hypertonia, hypotonia, excitability and lethargy) that have been normatively described for both substance exposed and non-exposed infants (Tronick, 2004). Exploratory data analysis techniques will be used to determine distributions for each measure to determine how many of these will be used in the final analysis.

*Breastmilk variables:* Concentrations of B+N and major metabolites in breast milk, maternal and infant plasma

b. Statistical plan including sample size justification and interim data analysis.

*Fetal studies:* Individual analyses will be performed for three cardiac measures (FHR, FHR variability and accelerations) and two motor variables (overall activity, bout duration), and two synthetic measures (event and time series-based FM-FHR coupling, as described in the Procedures section. We will also evaluate effects of BN on maternal physiological function (heart period, respirations, cardiac vagal tone, skin conductance, and blood pressure).

Models for aims 1 and 2 will be longitudinal mixed effects linear regression models with random intercepts (Fitzmaurice, 2011). Additional models with fetal sex interactions will be fit to evaluate whether boys are differentially affected by either exposure, as we have observed in previous evaluating neurobehavior in methadone exposed infants (Jansson, 2010). Additionally, all analyses will be adjusted for maternal age, race, and non-opioid substance use.

For Hypothesis 1A, we will fit a model where the outcome for the  $i$ th individual at the  $j$ th timepoint ( $y_{ij}$ ) =  $\beta_0 + \beta_1 \text{peak} + \beta_2 \text{p}_2 - \text{p}_1 + \epsilon_{ij}$ , and  $\beta_1$  represents the difference, across timepoints, in the outcome between peak and trough measurements. For Hypothesis 1B, we will fit a similar model,  $y_{ij} = \beta_0 + \beta_1 \text{peak} + \beta_2 \text{time} +$

$\beta_3\text{peak} * \text{time} + \beta_4 \cdot \text{pX4\_p} + \varepsilon_{ij}$ , where  $\beta_3$  represents the rate of change in the difference in outcome between peak and trough over time. For Hypothesis 1C, we will fit a model where  $y_{ij} = \beta_0 + \beta_1\text{peak} + \beta_2\text{BN} + \beta_3\text{peak} * \text{BN} + \beta_4 \cdot \text{pX4\_p} + \varepsilon_{ij}$ , where  $\beta_3$  represents the between-treatment (BN-Methadone) or (BN-Buprenorphine) difference in peak-trough differences. Additionally, we will fit a model with a 3-way interaction between peak, time, and BN to determine if changes over time in peak-trough differences vary between BN and Buprenorphine.

For Hypothesis 2A, we will fit models separately for peak and trough measures where  $y_{ij} = \beta_0 + \beta_1\text{BN} + \beta_2 \cdot \text{pX2\_p} + \varepsilon_{ij}$  where  $\beta_1$  represents the difference in outcome between BN and Bup. We will also fit models where  $(y_{ij}) = \beta_0 + \beta_1\text{BN} + \beta_2\text{time} + \beta_3\text{BN} * \text{time} + \beta_4 \cdot \text{pX4\_p} + \varepsilon_{ij}$ , and  $\beta_3$  represents the difference in outcome trajectory over time between BN and Buprenorphine. For Hypothesis 2B, we will fit a model similar to 2A but only using data from 36 weeks to compare methadone and BN.

*Neonatal study:* For hypothesis 3A, we will use descriptive statistics to characterize NAS in BN-exposed infants, as measured by mean daily NAS scores on days 1-4 of life, highest NAS score, amount of medication (morphine sulfate, mg) required to treat NAS, number of days treated for NAS, and total days hospitalization. For hypothesis 3B, we will fit models of NAS severity (measured by Day 3 Finnegan scores, total medication used to treat NAS, total days of NAS treatment and total days of hospitalization), as a function of BN exposure (compared to methadone exposure), adjusting for maternal age, race, and non-opioid substance use. The models for hypothesis 3C will be analogous, but with buprenorphine exposure as the comparator. For hypothesis 3D, we will examine additional predictors of NAS severity including infant sex (Warren, 2015), daily and cumulative dose of BN, other medications including SSRIs (dosage and categorical), illicit drug use based on number of “dirty” urines and specific substance exposures, cigarette smoking (cigarettes per day and CO levels).

*Infant study:* For hypothesis 4A, we will use descriptive statistics to characterize BN-exposed infants' NNNS scores on each of 13 summary scales; based on previous work we will focus on habituation, arousal, excitability, and hypertonicity. We will fit a model to determine if NNNS scores change over time during the first month of life, and we will fit an additional model with an interaction between infant sex and time to determine if sex affects NNNS trajectories. For hypothesis 4B, we will fit models where  $\text{NNNS}_{ij} = \beta_0 + \beta_1\text{BN} + \beta_2 \cdot \text{pX2\_p} + \varepsilon_{ij}$ , and  $\beta_1$  represents the difference, across timepoints in the NNNS between BN and methadone exposed infants. We will then fit a model where  $\text{NNNS}_{ij} = \beta_0 + \beta_1\text{BN} + \beta_2\text{time} + \beta_3\text{BN} * \text{time} + \beta_4 \cdot \text{pX4\_p} + \varepsilon_{ij}$ , where  $\beta_3$  represents the difference in NNNS trajectories over time between BN and methadone-exposed infants. For hypothesis 4C, we will fit analogous models to 4B, but with buprenorphine-exposed infants as the comparator. These models will be adjusted for maternal age, race, dosing, and other substance use.

*Breastmilk study:* Basic descriptive statistics (mean, standard deviation, range) will be used to report concentrations of B+N in breast milk of lactating women on days 2-4, 14 and 30. Additional considerations for associations between maternal dose, maternal plasma and breast milk concentrations will be examined using linear regression. Descriptive statistics will be used to report plasma concentrations of B+N in breastfeeding infants and linear regression to evaluate potential associations between infant B+N plasma concentrations and maternal B+N dose. Although potentially underpowered, we will also fit linear regression models for associations between maternal dose, maternal plasma concentrations and breast milk concentrations with maternal dose as the main predictor. Although limited power exists for longitudinal models in this study due to small subject numbers, we will fit mixed effects models to examine changes over time in breast milk B+N concentrations for each sampling time. The analyses proposed here are not meant to be exhaustive and cannot be due to space limitations. However, they illustrate our approach for examining the relations among the complex set of independent, dependent, and confounding variables collected in this proposal.

*Computation of Power:* Sample size estimates for each study were premised with a power of .8, alpha =.05, and large effect sizes as observed in our prior studies (Jansson, 2005, 2007a), which were conducted with a similar experimental design. Based on a conservative estimate of 50% non-completion, the total number of participants to be enrolled will be 160. In comparison samples, we will have 40 for buprenorphine, and 40 for methadone. Using available pilot data, for hypothesis 1, we would have 80% power to detect a mean difference of 4.23 (SD 6.68) in peak/trough fetal heart rate. For the mixed effects models, via simulation using pilot data, we would be powered to detect a trajectory difference of .35 per week between groups. For hypothesis 2, we would have 80% power to detect a mean difference of 4.12 (SD 6.49) in peak fetal heart rate. For the mixed effects models, via simulation, we would be powered to detect a trajectory difference of .32 per week between BN and buprenorphine.

For hypothesis 3, we would have 80% power to detect a mean effect size of ..63 for difference in NAS severity between groups

For hypothesis 4, we would have 80% power to detect a group difference of .44 (SD 0.70) in NNNS subscales scores. For the mixed effects models, via simulation using pilot data on the arousal subscale, we would be powered to detect a trajectory difference of .04 per day between groups.

No interim data analysis is planned for this study.

c. Early stopping rules.

The study may be modified, suspended, or terminated at the recommendation of the Johns Hopkins IRB or at the direction of the DSMB in the interests of protecting study participants. Reasons the JHU IRB or DSMB may recommend modification, suspension, or discontinuation of the trial could be based on the AE or SAE reports or the failure to maintain any participants in the study due to premature attrition during induction with buprenorphine.

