#### **4. Study Procedures**

##### **a. Study design, including the sequence and timing of study procedures:**

No procedures described here are part of routine patient care.

Participants will be selected from a population of women with OUDs in substance use disorder treatment at the Center for Addiction and Pregnancy (CAP), a comprehensive care treatment facility located in Baltimore and providing treatment for substance use disorders, mental health services, obstetric care and pediatrics (Jansson, 1996), which has been the site for all previously described research activities. Additional participants may include stable pregnant patients who are maintained on B+N in treatment by other providers who are willing to leave weekly research urines for toxicology testing and undergo fetal testing procedures. Total subject enrollment will be 160 (80 methadone and 80 B+N) participants; using a conservative estimate of 50% non-completion, the final sample size will be 80 (40 methadone and 40 B+N) mother/infant dyads.

Women accepting or requesting buprenorphine treatment will be offered study participation at the time of their contact with CAP intake staff after indicating a willingness to talk to study staff regarding research. The methadone comparison sample ( $n=80$ ) will be drawn from the population of CAP methadone maintained women and matched on . severity of OUD (route of administration (IV vs other) Eligibility for study enrollment and B+N maintenance will be determined by the project obstetrician and psychiatrist prior to study enrollment. B+N dose after induction to medication will be determined and regulated by the psychiatrist with adjustments made at the recommendation of patient counselors based on subjective and objective indicators of withdrawal or over-medication symptoms. All medication dosing will take place at an observed medication window. Take-home dosing will be afforded for holidays, inclement weather, or at the discretion of the project psychiatrist with input from the subject's counselor for other reasons on an individualized basis. Participants enrolled from other treatment programs will be informed of the study at their treatment program and asked to contact study personnel if they are interested.

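### Random intercepts alone can misstate the standard errors of the peak and trajectory tests in Aims 1 and 2, in either direction, by an amount the plan's figures cannot settle

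*Combined protocol and SAP*

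**What the plan says.** Section 7b of the combined protocol and SAP (fetal studies) states: "Models for aims 1 and 2 will be longitudinal mixed effects linear regression models with random intercepts". It names no random effect for peak or gestational age, no day-within-woman effect, no residual covariance structure and no robust standard error.

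The tests that depend on this are defined in the same section. The H1c coefficient "represents the between-treatment (BN-Methadone) or (BN-Buprenorphine) difference in peak-trough differences", and the H2a interaction coefficient "represents the difference in outcome trajectory over time between BN and Buprenorphine". H1a tests the peak effect and H1b the peak-by-time effect. A further model has a peak-by-time-by-group interaction.

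Section 4b gives the data structure: up to eight one-hour sessions per woman, two on each of four days (24, 28, 32 and 36 weeks), with fewer days for women who enrol after 24 weeks. Under Computation of Power: "Sample size estimates for each study were premised with a power of .8, alpha =.05, and large effect sizes". On group sizes, section 4a says "the final sample size will be 80 (40 methadone and 40 B+N) mother/infant dyads", and section 7b says "In comparison samples, we will have 40 for buprenorphine, and 40 for methadone".

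**The concern.** A random intercept lets women differ in overall level and otherwise treats a woman's eight recordings as exchangeable. The tests listed above are not about level. They are about within-woman effects, or group differences in such effects, and their standard errors depend on variance components that the stated model sets to zero.

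Two departures matter, and they pull in opposite directions for the peak tests:

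- If women differ in their own response to the peak dose, or in their own slope over gestation, the model counts each day as fresh evidence on that effect. The standard error is too small.
- If the two recordings of a day share variation (the state of mother or fetus that day), that variation cancels from the peak-trough difference but stays in the model's residual variance. The standard error of the peak contrast is too large.

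The protocol makes both plausible. Doses are individualised and effects by fetal sex are anticipated. Same-day influences such as meals, smoking and substance use are controlled because they are thought to affect a recording. At stake is whether H1a to H1c and the H2a trajectory comparison are declared too readily or a real effect is missed.

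**Working it through.** **The plan's own figure.** Section 7b gives 80% power for a difference of 4.23 (SD 6.68). For two groups at two-sided 5%, n = 2 × (1.96 + 0.842)² × (6.68/4.23)² = 15.70 × 2.494 = 39.2, so 40 per group. Power at 40 is 80.8% (normal) or 79.9% (t-test). Enrolment is 80/(1 − 0.5) = 160, as the plan says ("Based on a conservative estimate of 50% non-completion, the total number of participants to be enrolled will be 160"). Both figures reproduce. The power figure matches a simple comparison of one value per woman, so it gives no information on how the variance splits between women, days and sessions.

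**Inputs for the check.** From the documents: four days, two sessions a day, 40 women per group, alpha 0.05. Assumed, because the documents do not give them:

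- τ², the variance between women in the true peak-trough difference;
- σ², the session variance;
- ω², the day variance shared by a day's two sessions.

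A single-day difference has variance τ² + 2σ². The share τ²/(τ² + 2σ²) is what is varied below.

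**H1c, four days.** Per woman:

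- true variance of the mean difference: τ² + σ²/2;
- variance the random-intercept model uses: (7σ² + 2τ² + 6ω²)/14 = σ²/2 + τ²/7 + 3ω²/7;
- R = true / model variance, and type I error = 2Φ(−1.96/√R).

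With the single-day variance set to 1:

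| Stable share | Day variance | True | Model | √R | Type I error |
|---|---|---|---|---|---|
| 10% | 0 | 0.325 | 0.239 | 1.17 | 9.3% |
| 25% | 0 | 0.4375 | 0.223 | 1.40 | 16.2% |
| 50% | 0 | 0.625 | 0.196 | 1.78 | 27.2% |
| 0 | 0 | 0.250 | 0.250 | 1.00 | 5.0% |
| 0 | 0.5σ² | 0.250 | 0.357 | 0.84 | 1.9% |
| 0 | σ² | 0.250 | 0.464 | 0.73 | 0.8% |
| 20% | σ² | 0.400 | 0.400 | 1.00 | 5.0% |
| 50% | σ² | 0.625 | 0.304 | 1.43 | 17.2% |

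R is scale-free, so the SD of 6.68 plays no part in these results. As the share tends to 100% with no day variance, R tends to 7 and type I error to about 46%.

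**Two days instead of four.** True variance is τ² + σ² and model variance σ² + τ²/3. At a 50% share R = 0.75/0.4167 = 1.8, giving 14.4%.

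**Simulation.** With 4,000 balanced trials per setting, H1c at a 50% share gave 27.6%, and H1a gave 27.9%. In 250 REML fits per setting, adding a random peak effect changed the H1c error as follows:

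- 50% share, four days: 29.6% to 4.0%;
- 50% share, one to four days per woman: 22.4% to 4.8%;
- 25% share, one to four days per woman: 11.6% to 7.2%.

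The Monte Carlo SE is about 1.4 points at 5%.

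**H2a trajectory, separate peak or trough models, four days.** Let k be the between-woman slope variance divided by the sampling variance of one woman's slope. Then R = (1 + k)/(1 + k/3). For k = 0, 0.5, 1 and 2, type I error is 5.0%, 8.4%, 11.0% and 14.4%, with a limit of 25.8%.

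**H1b needs its own term.** Take a 50% share, a single-day SD of 6.68 and an assumed between-woman SD of 0.5 per week in the peak-by-time effect. On the daily differences, with a random peak effect only, the slope sampling variance is (0.5 × 6.68²)/80 = 0.279. So k = 0.25/0.279 = 0.90, and H1b type I error is still about 10%.

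**The case against.** The strongest reply is that nothing in the documents shows the omitted variances to be material. With none, the standard errors are right. With both, they can offset: at a 20% share and day variance equal to session variance the error is exactly nominal. Late enrolment, and days cancelled for positive urine screens, also reduce the number of days per woman and with it any inflation. All of this stands, and it is why the point is conditional.

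A second reply is that section 7b calls its analyses illustrative, not exhaustive, and that the printed equations do not show even the random intercept. The equations are partly unreadable in the text available, so nothing here rests on them. But a general caveat does not supply a different covariance structure for models whose structure the plan states in words.

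A third reply is that the scope is narrower than all of Aims 1 and 2. That also stands. H2b uses 36-week data only. The H2a average group difference is a between-woman comparison, which the random intercept serves.

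**Conclusion.** The point holds in conditional form. The stated model gives correct standard errors for H1a, H1b, H1c, the three-way test and the H2a trajectory only if the omitted variances are zero or happen to cancel, and the plan reports nothing that shows either. Under the assumptions above, H1c's real type I error could lie anywhere from below 1% to 27% or more.

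Three stronger readings are tempting, and the documents do not support them:

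- A reader might infer that the standard errors are wrong and the p-values invalid. The documents show only that they may be.
- A reader might take 27% as a maximum or as a figure from the plan. It is neither. It needs a 50% stable share, no day variance and four complete days for every woman.
- A reader might extend the point to Aim 4, where the trajectory coefficient "represents the difference in NNNS trajectories over time between BN and methadone-exposed infants". Section 7b limits random intercepts to Aims 1 and 2 and states no random-effects structure for the NNNS models. There, the structure simply remains to be specified.

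**What to change.** Specify one of the following in section 7b before the data are analysed.

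- **Simplest, and covers every affected test:** keep the random intercept and base inference on small-sample cluster-robust standard errors by woman, for example CR2 with Satterthwaite degrees of freedom.
- **Model-based alternative:** where peak and trough are pooled, add per-woman random effects for peak and gestational age, a woman-by-day intercept and, for H1b and the three-way test, a random peak-by-time effect. In the separate peak and trough trajectory models, add a random time slope. Use Kenward-Roger or Satterthwaite degrees of freedom, with the cluster-robust standard errors as the named fallback if a model does not converge.

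Reporting the pilot variance components would show which departure matters.

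The cost is some wording and a few lines of code, with no new visits or participants. Intervals may widen materially if heterogeneity is large (SE ratio about 1.2 to 1.8 for shares of 10% to 50%), and may narrow if day variance dominates and is modelled. If 6.68 is read as the SD of a single-day difference, which the text leaves open, the widening need not undercut the stated H1 power. At a 50% share, a woman's four-day mean difference has 62.5% of the variance that the one-value-per-woman calculation used.
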